5.10.3.4 Statistical Methods – Health Economics Analysis

No health economic evaluation is planned, but the collection of EQ5D would allow Quality Adjusted Life Years (QALYs) to be calculated.

5.11 Data Monitoring

5.11.1 Independent Data Monitoring Committee

To ensure the safety and efficacy and overall trial conduct, an IDMC will be established and take part in the data monitoring. The IDMC will consist of members with specific expertise in ophthalmology and molecular genetics. The IDMC will make recommendations on the safety data prior to any dose changes in the dose escalation phase, and prior to the enrolment of the first participant in the dose expansion phase.

Further details of the roles and responsibilities of the IDMC, including membership, relationships with other committees, decision making processes, and the timing and frequency of interim analyses (and description of stopping rules and/or guidelines where applicable) are described in detail in the CNGB3 Gene Therapy Trial for Achromatopsia IDMC Charter).

5.11.2 Interim Analyses

No formal interim analysis is planned within the trial, but periodic reports concerning participant safety and key efficacy outcomes will be prepared for the IDMC as agreed in the IDMC charter.

5.11.3 Data Monitoring for Harm

5.11.3.1 Safety reporting

██████████ will be responsible for pharmacovigilance services.

Definitions of harm of the EU Directive 2001/20/EC Article 2 based on the principles of ICH GCP apply to this trial.

CNGB3 Gene Therapy trial for Achromatopsia

Table 3: Adverse Event Definitions

Adverse Event (AE)	Any untoward medical occurrence in a clinical trial participant administered a medicinal product and which does not necessarily have a causal relationship with this product.
Adverse Reaction (AR)	Any untoward and unintended response to an investigational medicinal product related to any dose administered This includes medication errors, uses outside of protocol (including misuse and abuse of product)
Unexpected Adverse Reaction (UAR)	An adverse reaction, the nature or severity of which is not consistent with the applicable product information (eg Investigator’s Brochure for an unauthorised product or summary of product characteristics (SPC) for an authorised product.
Serious Adverse Event (SAE) or Serious Adverse Reaction (SAR)	Any AE or AR that at any dose: 
 • results in death • is life threatening* • requires hospitalisation or prolongs existing hospitalisation** • results in persistent or significant disability or incapacity • is a congenital anomaly or birth defect • or is another important medical condition***
SUSAR	Suspected Unexpected Serious Adverse Reaction

* the term life threatening here refers to an event in which the participant is at risk of death at the time of the event; it does not refer to an event that might hypothetically cause death if it was more severe (e.g., a silent myocardial infarction)
 
** Hospitalisation is defined as an in-patient admission, regardless of length of stay, even if the hospitalisation is a precautionary measure for continued observation. Hospitalisation for pre-existing conditions (including elective procedures that have not worsened) do not constitute an SAE
 
*** Medical judgement should be exercised in deciding whether an AE or AR is serious in other situations. Important AEs or ARs that may not be immediately life threatening or result in death or hospitalisation but may seriously jeopardise the participant by requiring intervention to prevent one of the other outcomes listed in the table (e.g., a secondary malignancy, an allergic bronchospasm requiring intensive emergency treatment, seizures or blood dyscrasias that do not require hospitalisation, or development of drug dependency).
	

Adverse events include:

- an exacerbation of a pre-existing illness
- an increase in the frequency or intensity of a pre-existing episodic event or condition
- a condition (regardless of whether PRESENT prior to the start of the trial) that is DETECTED after trial drug administration. (This does not include pre-existing conditions recorded as such at baseline – as they are not detected after trial drug administration.)

CNGB3 Gene Therapy trial for Achromatopsia

- continuous persistent disease or a symptom present at baseline that worsens following ATIMP administration

Adverse events do NOT include:

- Medical or surgical procedures: the condition that leads to the procedure is the adverse event
- Pre-existing disease or a condition present before ATIMP administration that does not worsen
- Hospitalisation where no untoward or unintended response has occurred e.g. elective cosmetic surgery
- Overdose of medication without signs or symptoms

5.11.3.2 Other Notifiable Adverse Events

In order to manage the safety risks associated with administration of the ATIMP, all safety events will be reviewed within a short time frame for all participants, as described in the CNGB3 Gene Therapy Trial for Achromatopsia Data Management Plan.

Pregnancy is the only additional notifiable event that requires expedited reporting.

5.11.3.3 Procedures to follow in the event of female participants becoming pregnant

A pregnancy test will be conducted for all females of child bearing age and the results will be recorded in the medical notes before enrolling a volunteer to the trial. Females with a positive pregnancy test at this point will be excluded from the trial.

A further pregnancy test will be performed on the day of administration of the ATIMP. Female participants with a positive pregnancy test at this point will be excluded from the trial prior to administration of the ATIMP.

Although participants are instructed to use double barrier contraception, we cannot exclude entirely that a participant might become pregnant after administration of the ATIMP. In the unlikely event that a participant is found to be pregnant we will notify their GP that she is participating in a gene therapy trial and that, although the risks involved are minimal, there is a chance of gene transfer to the unborn child. With the participant's consent, we will ask the GP/obstetrician to provide us with regular reports about the pregnancy until delivery. The pregnancy will be reported to [REDACTED] on a pregnancy report form within 24 hours of the investigator becoming aware of the event. The participant will continue to be assessed until outcome of the pregnancy. However, if the participant is unable or unwilling to participate further in the trial, she will be encouraged to continue clinical monitoring visits to assess ocular health. In this situation, we may choose to enrol another participant to ensure the scientific validity of the trial.

5.11.3.4 Procedures to follow in the event of the partners of male participants becoming pregnant

Although participants are instructed to use double barrier contraception, we cannot exclude entirely that the partner of a participant might become pregnant after administration of the ATIMP. In the unlikely event that this occurs we will notify the participant's GP that he is participating in a gene therapy trial and that, although the risks involved are minimal, there is a chance of gene transfer to

CNGB3 Gene Therapy trial for Achromatopsia

the unborn child. With the participant’s consent, we will contact the partner to ascertain the status of the pregnancy and the outcome. The pregnancy will be reported to [REDACTED] on a pregnancy report form within 24 hours of the investigator becoming aware of the event.

5.11.3.5 Investigator responsibilities relating to safety reporting

The Investigator will assume overall responsibility for evaluating and reporting adverse events. In urgent situations, a member of the trial team may report on their behalf, while making every effort to discuss the event with them. All non-serious AEs and ARs, whether expected or not, should be recorded in the participant’s medical notes, including all events observed following ATIMP administration, and in eCRF. These should be entered on to the database according to the timelines defined in the CNGB3 Gene Therapy trial for Achromatopsia Data Management Plan to allow appropriate monitoring by the CMT. SAEs and SARs should be notified to [REDACTED] immediately the investigator becomes aware of the event (in no circumstance should this notification take longer than 24 hours).

Clinically significant abnormalities in the results of objective tests will also be recorded as adverse events. If the results are not expected as part of disease or surgery these will also be recorded as unexpected. There are currently no expected events associated with the ATIMP.

All serious adverse events will be recorded in the hospital notes and the eCRF. Adverse events will be recorded with clinical symptoms and accompanied with a simple, brief description of the event, including dates as appropriate. All adverse events will be recorded until the end of the trial (refer to Section 5.6.3 for definition), or until pregnancy outcome in the case of pregnancy. All SAEs will be recorded, fully investigated and appropriately managed until resolution or stabilisation and CI sign off.

5.11.3.5.1 Seriousness assessment

When an AE or AR occurs, the investigator responsible for the care of the participant must first assess whether or not the event is serious using the definition given in Table 3. If the event is classified as ‘serious’ an SAE form must be completed and emailed to [REDACTED] (or delegated body) notified within 24 hours of the investigator becoming aware of the event.

5.11.3.5.2 Severity or grading of Adverse Events

The severity of all AEs and/or ARs (serious and non-serious) in this trial should be graded using the toxicity grading in NIH CTCAE Version 4.0 (NIH, 2009).

Table 4: Grading of Adverse Events

Category	Definition
Mild (Grade I)	Asymptomatic or mild symptoms; clinical or diagnostic observations only; intervention not indicated
Moderate (Grade II)	Minimal, local or non-invasive intervention indicated; limiting age appropriate instrumental ADL*
Severe (Grade III)	Severe or medically significant but not immediately life threatening; hospitalisation or prolongation of hospitalisation indicated; disabling; limiting self-care ADL**
Grade IV	Life threatening consequences; urgent intervention indicated
Grade V	Death related to AE

CNGB3 Gene Therapy trial for Achromatopsia

* Instrumental ADL (Activities of Daily Living) refer to preparing meals, shopping for groceries or clothes, using the telephone, managing money, *etc*

**Self-care ADL refer to bathing, dressing and undressing, feeding self, using the toilet, taking medications, and not bedridden.

5.11.3.5.3 Causality

Causality will be assessed in terms of both the ATIMP and the surgical procedures. Based on all available information at the time of completion of the case report form, the investigator must assess the causality of all serious events or reactions. It is of importance in this trial to capture and differentiate events related to:

- The ATIMP administration surgery
- The ATIMP

The differentiated causality assessments will be captured in the trial specific CRF and SAE form. If the event is related to the ATIMP, definitions in Table 5 will be used to capture the information. Any event that is only related to the ATIMP administration surgery will be classified as an Adverse Event.

Table 5: Causality definitions

Relationship	Description	Event Type
Unrelated	There is no evidence of any causal relationship	Unrelated SAE
Unlikely to be related	There is little evidence to suggest that there is a causal relationship (e.g., the event did not occur within a reasonable time after administration of the trial medication). There is another reasonable explanation for the event (e.g., the participant's clinical condition or other concomitant treatment)	Unrelated SAE
Possibly related	There is some evidence to suggest a causal relationship (e.g., because the event occurs within a reasonable time after administration of the trial medication). However, the influence of other factors may have contributed to the event (e.g., the participant's clinical condition or other concomitant treatment)	SAR
Probably related	There is evidence to suggest a causal relationship and the influence of other factors is unlikely	SAR
Definitely related	There is clear evidence to suggest a causal relationship and other possible contributing factors can be ruled out.	SAR

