Primary Outcome(s)	
The primary outcome is safety of subretinal administration of AAV2/8-hCARp.hCNGB3.
 
Safety is defined as the absence of ATIMP-related:
 
 Reduction in visual acuity by 15 ETDRS letters or more Severe unresponsive inflammation Infective endophthalmitis Ocular malignancy Grade III or above non-ocular SUSAR 
Safety will be assessed for 6 months after the intervention in this study, and a further 4.5 years in a separate subsequent study.

Key Secondary Outcomes	
The secondary outcomes are measures of the efficacy of the intervention, which will be performed on an individual participant basis and will be descriptive in nature. Efficacy will be assessed at several time points between 3 to 6 months after the intervention:
 
 Any improvement in visual function from baseline that is greater than the test-retest variation for that test and is sustained for at least two consecutive assessments. Any improvement in retinal function from pre intervention that is greater than the test-retest variation and measurable by electroretinography (ERG). Quality of life measures.

Gene Therapy for Achromatopsia (CNGB3)

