4.1.5.5 Risk of surgical adverse effects

The risk of significant surgical adverse effects is similar to the standard surgical care for other common forms of vitreo-retinal disorders. To manage the risk of surgical adverse events, only highly experienced surgeons will perform the procedure. Complications of surgery are typically managed effectively by medication or further surgical intervention but can rarely result in lasting harm to sight. The risk of lasting severe impairment of sight from vitrectomy surgery is approximately 1 in 1000. We have identified some reduction in outer retinal thickness and deterioration in acuity in 2 of the 12 participants in our previous clinical trial, believed to result from temporary retinal detachment which is a deliberate consequence of targeted administration of the vector suspension, but no other significant surgical adverse effects.

Delivery of ATIMP to the subretinal space will be performed by standard surgical vitrectomy. This will involve a 3-port pars plana vitrectomy followed by injection of ATIMP using a fine cannula through small retinotomies, resulting in a temporary retinal detachment. Previous gene therapy clinical trials have shown that the bleb of subretinal ATIMP suspension can be expected to resolve spontaneously over the course of the first 24 to 48 hours postoperatively as the fluid is absorbed by the underlying retinal pigment epithelium.

Gene Therapy for Achromatopsia (*CNGB3*)

Potential complications of surgery specifically include persistence of the subretinal vector bleb, the development of retinal tears, and persistent postoperative intraocular inflammation. We will minimise any risk to visual function by limiting ATIMP delivery to the area of retina most likely to benefit, and by leaving the contralateral eye untreated. Retinal detachment caused by persistent vector bleb or intraoperative retinal tear is expected to occur in fewer than 1 in 100 procedures and can be effectively managed in the majority by retinopexy, with or without intraocular tamponade. Vitrectomy surgery is a standard technique, commonly performed for a wide range of indications. Injection of fluids under the retina is less commonly performed but is a standard step in surgery for subretinal haemorrhage, and an adjunctive technique in the management of retinal detachment.

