5.5 Outcomes

5.5.1 Primary Outcomes

The primary outcome is defined as any of the below occurring during the 6 weeks following administration, at least possibly related to the ATIMP, not surgery alone:

- Reduction in visual acuity by 15 ETDRS letters or more

Gene Therapy for Achromatopsia (*CNGB3*)

- Severe unresponsive inflammation
- Infective endophthalmitis
- Ocular malignancy
- Grade III or above non-ocular SUSAR (see section 5.11.3)

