5.10.3.2 Statistical Methods – Primary Outcome Analysis

The primary outcome is safety of subretinal administration of the ATIMP defined as any of the below occurring during the 6 weeks following administration, at least possibly related to the ATIMP, not surgery alone:

- Reduction in visual acuity by 15 ETDRS letters or more
- Severe unresponsive inflammation
- Infective endophthalmitis
- Ocular malignancy
- Grade III or above non-ocular SUSAR (see section 5.11.3)

The number of DLEs at each dose level will be summarised by cohort and overall.

It is anticipated that the ATIMP will be administered at the MTD in up to 15 participants (6 adults in the dose escalation phase and up to 18 further adults and children in the confirmatory safety phase). Safety data relating to these participants will allow estimation of an upper bound for the true event rate through a 95% confidence interval.

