2. OUTCOME DEFINITIONS

2.1. Primary Safety Outcome

The primary safety outcome is defined as any of the below events occurring during the 6 weeks following administration, at least possibly related to the ATIMP, not surgery alone:

• Reduction in visual acuity by 15 Early Treatment Diabetic Retinopathy Study (ETDRS) letters or more

- Severe unresponsive inflammation (defined in Section 4.2 of the protocol)
- Infective endophthalmitis
- Ocular malignancy
- Grade III or above non-ocular suspected unexpected serious adverse reaction (SUSAR) (Protocol MGT006, Section 5.11.3.4.2 Severity or Grading of Adverse Events).

This is the same criteria as the dose limiting event in the dose escalation phase.

Overall safety will be assessed for 6 months after the intervention in this study, and a further 4.5 years in a separate long-term follow-up study (Protocol MGT007).

The adverse events preferred terms are identified in a separate file (AES_OF_INTEREST.xlsx) and saved in the ERIS system.

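### The primary safety outcome leaves out harm judged to come from surgery alone, and no SAP output counts 15-letter losses in treated eyes regardless of cause

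*Protocol*

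**What the plan says.** **The outcome.** Protocol 5.5.1 lists five components: a loss of 15 or more ETDRS letters, severe unresponsive inflammation, infective endophthalmitis, ocular malignancy, and a non-ocular SUSAR of Grade III or above. They count when "occurring during the 6 weeks following administration, at least possibly related to the ATIMP, not surgery alone". Protocol 5.10.3.2 repeats the condition. SAP 2.1 does too ("The primary safety outcome is defined as any of the below events occurring during the 6 weeks following administration"), and says the criteria are the same as for a dose-limiting event.

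**Its name.** Protocol 1.3: "The primary outcome is safety of subretinal administration of AAV2/8-hCARp.hCNGB3". Protocol 5.10.3.2: "The primary outcome is safety of subretinal administration of the ATIMP". The primary objective is narrower: Protocol 4.2.1 and SAP 1.1 speak of the safety of the vector.

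**Attribution.** The trial is open label (Protocol 4.3). Protocol 5.11.3.5.3 asks for causality to be judged against both the ATIMP and the surgery, and adds that "the investigator must assess the causality of all serious events or reactions". Events related only to the surgery are classed as adverse events.

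**Expected surgical events.** Protocol 5.11.3.5.4 includes temporary or mild acuity loss, as far as hand movements, lasting up to 8 weeks.

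**Earlier experience.** Protocol 4.1.5.5 reports "deterioration in acuity in 2 of the 12 participants in our previous clinical trial, believed to result from temporary retinal detachment", the detachment being an intended part of delivery.

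**Planned outputs.** SAP 5.1 gives the proportion with the primary outcome and a 95% CI by age group, dose and overall. SAP 5.2 tabulates adverse events, including by relationship to the ATIMP and to the surgery. SAP 6.2 summarises and plots visual acuity.

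**The concern.** The product reaches the retina only through vitrectomy and a deliberate detachment (Protocol 4.1.5.5 and 5.4.1.4). Harm from delivery therefore falls within the outcome as Protocol 1.3 and 5.10.3.2 name it, but outside what is counted.

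Whether an event counts rests on a judgement that the trial data cannot test. Every participant receives vector and surgery together in one eye (Protocol 5.9.1). The comparator is the other eye (Protocol 4.1.6), which receives neither. No masked or independent adjudication of causality is described. The IDMC reviews safety data, but its charter is not among the documents.

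At stake is how the headline proportion is read. A figure at or near zero could be taken to mean that treated eyes did not lose vision, when it means only that no loss was attributed, even possibly, to the vector.

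**Working it through.** The documents state no power or calculated sample size for this outcome, so there is no figure of the plan's own to reproduce. The check compares passages and then gives an illustration.

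**Step 1. Can a qualifying loss be left out?** The outcome window is 6 weeks. The listed surgical acuity loss may last up to 8 weeks and may reach hand movements. A drop of 15 letters or more within the window can therefore match a listed surgical event in both depth and timing. If the investigator judges it surgery alone, it is not counted.

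**Step 2. Does another output supply the missing count?**

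| SAP section | Output | Cause-free count of treated eyes losing 15 letters or more? |
|---|---|---|
| 5.1 | Primary outcome; similar analysis for dose-limiting events | No: both need attribution |
| 5.2 | Adverse events overall, by severity, by relationship to ATIMP and to surgery | No: by event term, with no letter threshold stated |
| 6.2 | Acuity by age group, dose and time point; individual plots of treated against untreated eye | No: no responder or loss category specified |

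**Step 3. Illustration from the earlier trial.** Input: 2 of 12 (Protocol 4.1.5.5). Assumptions: both losses reached 15 letters within 6 weeks, both were judged surgery alone, and nothing else qualified. The protocol gives neither the size nor the timing of the losses.

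- Rule as defined: 0/12. Exact (Clopper-Pearson) upper limit = 1 − 0.025^(1/12) = 26.5%.
- Regardless of attribution: 2/12 = 16.7%, exact 95% CI 2.1% to 48.4%.

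**Step 4. Scaled to 36 participants (maximum in Protocol 5.7).** At a rate of 1/6, 36 × 1/6 = 6 such losses are expected, and P(at least one) = 1 − (5/6)^36 = 99.9%. At lower assumed rates P(at least one) is 53% (rate 2.1%), 84% (5%) and 98% (10%). If 6 occurred, a cause-free count gives 6/36 = 16.7%. The SAP 5.1 interval is 0.167 ± [1.96 × √(0.167 × 0.833/36) + 1/72], or 3.1% to 30.2%; the exact interval is 6.4% to 32.8%. If all 6 were judged surgery alone, the primary outcome gives 0/36, with a SAP upper limit of 1/72 = 1.4% (exact 9.7%).

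**Step 5. How far does a zero depend on attribution?** Let f be the share of such losses called at least possibly ATIMP-related. At the 1/6 rate, P(zero counted) = (1 − f/6)^36:

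| f | P(zero counted) |
|---|---|
| 0 | 100% |
| 0.25 | 21.6% |
| 0.50 | 4.4% |
| 1 | 0.1% |

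Setting this probability to 0.5 gives f = 6 × (1 − 0.5^(1/36)) = 0.11. At this rate a zero is more likely than not only if roughly nine in ten or more of these losses are judged surgery alone.

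**The case against.** **Restricting the outcome is a coherent choice.** The objective is safety of the vector. Protocol 1.3 itself goes on to define safety through ATIMP-related events, and the same definition drives dose escalation. This stands: it is a reason to leave the defined outcome alone. It does not supply the missing count or make the label accurate.

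**The threshold is inclusive.** Possibly related is enough, and Table 5 of Protocol 5.11.3.5.3 lets timing support that category even where other factors contributed. Shared-cause events count. This stands, and Step 5 shows its weight.

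**Surgical harm is reported elsewhere.** A reader might infer that harm from delivery could vanish from the report. The documents do not support that: SAP 5.2 tabulates adverse events by relationship to surgery and lists them, and SAP 6.2 shows acuity for each eye. Only the attributed proportion could be zero.

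**Causality is not clearly confined to serious events.** A reader might infer such a limit from "the investigator must assess the causality of all serious events or reactions". But the same section opens without it and places the assessments in the CRF as well as the SAE form, and SAP 5.2 needs them for all adverse events. At most the wording is ambiguous for a non-serious 15-letter loss.

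**Nor is the acuity component shown to rest on event terms alone.** SAP 2.1 says "The adverse events preferred terms are identified in a separate file", but that file is not available. SAP 2.1 does not say the letter criterion is derived only from it, and Protocol 5.11.3.5 has clinically significant test abnormalities recorded as adverse events. What can be said is that no rule linking measured letters to the outcome is stated.

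**An any-visit count would mislead.** Early loss is expected, and acuity on days 1 and 3 uses a previous refraction (Protocol 5.6, Table 2). This stands and shapes the fix.

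**Conclusion.** The concern holds as a gap in reporting and labelling. The primary proportion depends on unmasked attribution, excludes harm judged surgery alone, and can sit at or near zero while treated eyes lose 15 letters because of delivery. No specified SAP output gives the cause-free count that would reveal this.

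The size cannot be fixed from the documents. The contrast of 0/12 with 2/12 is an illustration on the assumptions in Step 3. It comes from a trial of another vector in another disease (Protocol 4.1.3 and 4.1.5.1), and the two intervals overlap widely. It should not be read as a predicted rate here. At that rate, a zero is likely only if nearly all such losses are judged surgery alone. At lower rates a zero may also arise because few losses occur.

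The change should be made, but the defined outcome is not invalid.

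**What to change.** Leave the defined primary outcome and the dose-escalation rule as they are.

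1. **SAP 5.1:** add a supplementary row, by dose and overall, giving the five components regardless of attribution. Derive the acuity component from recorded ETDRS letters in the treated eye, against the SAP 3.2 baseline. Show separately losses of 15 letters or more at any visit to Week 6, losses still present at Week 6, and losses still present at Week 24.
2. **Protocol 5.11.3.5.3:** state that causality to the ATIMP and to the surgery is recorded for every event meeting a component, serious or not.
3. **Protocol 1.3 and 5.10.3.2:** reconcile the name of the outcome with the objective in Protocol 4.2.1.

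The cost is small. Acuity is already scheduled at days 1 and 3 and at Weeks 1, 2, 4, 6, 12 and 24 (Protocol 5.6, Table 2), so no visit or test is added, only one supplementary row with its acuity breakdown and a short derivation. The attribution-free figure may look less favourable and will include expected post-operative loss, which is why the persisting losses need their own entries.
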